#### 4.2.13 Immunogenicity

A summary of immunogenicity results is provided showing the number and percentage of participants who develop detectable Anti-Drug Antibodies (ADAs) against AZD8853, based on the participants in the immunogenicity analysis set. The number of ADA evaluable patients in the treatment group is used as the denominator for percentage calculation. Participants and/or data excluded from the immunogenicity analysis set are presented in separate outputs.

The following categories are included in the summary table:

- ADA positive at baseline and/or post-baseline visits. The percentage of these participants in a population is known as ADA prevalence.
- Treatment-induced ADA positive (positive post-baseline and not detected at baseline).
- Treatment-boosted ADA positive (baseline ADA titer that was boosted greater than the variability of the assay (i.e.,  $\geq 4$ -fold increase)
- Treatment-emergent ADA positive (either treatment-induced ADA positive or treatment-boosted ADA positive). The percentage of these participants in a population is known as ADA incidence.
- ADA positive post-baseline and positive at baseline.
- ADA positive at baseline and not detected post-baseline.
- Persistent positive, defined as ADA negative at baseline and having at least 2 post-baseline ADA positive measurements with  $\geq 16$  weeks between first and last positive, or an ADA positive result at the last available post baseline assessment.
- Transient positive, defined as ADA negative at baseline and at least one post- baseline ADA positive measurement and not fulfilling the conditions for persistently positive.

[figure not shown]
Blood samples collected outside of the scheduled time window are summarized at the next nominal time point if that does not already have a value, otherwise it is presented in listings with data excluded from summary outputs.

ADA results will also be listed for participants included in the immunogenicity analysis set.

## 5 INTERIM ANALYSIS

### Substudy 1

In the efficacy expansions (Part C1 and Part C2) an interim analysis is performed after the 20th participant in each expansion has had the opportunity for 2 on-treatment RECIST v1.1 assessments or has discontinued or withdrawn from treatment. Enrolment will continue while this analysis is ongoing. The analysis will provide tolerability and safety data and will also provide a reasonable chance to determine if there is a lack of efficacy. CCI

## 7 APPENDICES

### 7.1 Appendix A RECIST

#### **Derivation of RECIST v1.1 Visit Responses**

For all participants, the RECIST v1.1 tumour response data is used to determine each participant's visit response according to RECIST version 1.1. It is also used to determine if and when a participant has progressed in accordance with RECIST version 1.1 and their best objective response to IP.

Baseline radiological tumour assessments are performed no more than 28 days before the start of IP and ideally as close as possible to the start of IP. Tumour assessments are performed 6 weeks after 1st IP then every 9 weeks, until week 52 then every 12 weeks until disease progression.

If an unscheduled assessment is performed, and the participant has not progressed, every attempt is made to perform the subsequent assessments at their scheduled visits. This schedule is followed in order to minimize any unintentional bias caused by some participants being assessed at a different frequency than other participants.

From the investigator's review of the imaging scans, the RECIST v1.1 tumour response data is used to determine each participant's visit response according to RECIST version 1.1. At each visit, participants are programmatically assigned a RECIST version 1.1 visit response of CR, PR, SD, or Progressive Disease, using the information from TLs, NTLs and new lesions and depending on the status of their disease compared with baseline and previous assessments. If a participant has had a tumour assessment that cannot be evaluated, then the participant is assigned a visit response of NE (unless there is evidence of progression in which case the response is assigned as Progressive Disease).

Please refer to [Table 10](#) for the definitions of CR, PR, SD and Progressive Disease.

RECIST v1.1 outcomes (i.e. PFS, ORR etc.) are calculated programmatically for the site investigator data (see last section of this Appendix) from the overall visit responses.

### **Target Lesions (TLs) – site investigator data**

Measurable disease is defined as having at least one measurable lesion, not previously irradiated, which is  $\geq 10$  mm in the longest diameter (LD), (except lymph nodes which must have short axis  $\geq 15$  mm) with computed tomography (CT) or magnetic resonance imaging (MRI) and which is suitable for accurate repeated measurements. A participant can have a maximum of five measurable lesions recorded at baseline with a maximum of two lesions per organ (representative of all lesions involved and suitable for accurate repeated measurement) and these are referred to as TLs. If more than one baseline scan is recorded, then measurements from the one that is closest and prior to first IP dose is used to define the baseline sum of TLs. It is the case that, on occasion, the largest lesion does not lend itself to reproducible measurement. In which circumstance the next largest lesion, which can be measured reproducibly, is selected.

All other lesions (or sites of disease) not recorded as TL are identified as NTLs at baseline. Measurements are not required for these lesions, but their status are followed at subsequent visits.

Note: For participants who do not have measurable disease at entry (i.e. no TLs) but have non-measurable disease, evaluation of overall visit responses are based on the overall NTL assessment and the absence/presence of new lesions (see section below for further details). If a participant does not have measurable disease at baseline, then the TL visit response is Not Applicable (NA).

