5.1 Inclusion Criteria

The below are the master inclusion criteria for all Substudies of the study; all participants must meet the criteria described in the relevant Substudy in addition to those described below. Where Substudy-specific criteria are more stringent than master study criteria, the Substudy-specific criteria take precedent.

Participants are eligible to be included in the study only if all of the following criteria apply:

Informed Consent

- 1. Capable of giving signed informed consent as described in Appendix A which includes compliance with the requirements and restrictions listed in the ICF and in this protocol.
- 2. Provision of signed and dated, written informed consent prior to any mandatory study-specific procedures, sampling, and analyses.
- 3. Provision of signed and dated written consent prior to collection of samples for collection o

Age

4. Participant must be at least 18 years of age inclusive, at the time of signing the informed consent.

Type of Participant and Disease Characteristics

- 5. Have a life expectancy of ≥ 12 weeks.
- 6. Participants must have at least one lesion, that qualifies as a RECIST v1.1 TL at baseline. Tumour assessment by CT scan or MRI must be performed within 28 days prior to treatment.
 - a) A previously irradiated lesion can be considered a TL if the lesion is well defined, measurable per RECIST v1.1, and has clearly progressed during or after most recent therapy.
 - b) Participants undergoing paired tumour biopsies must have additional NTLs that can be biopsied at acceptable risk as judged by the Investigator or if no other lesion is

deemed suitable for biopsy, then a RECIST v1.1 TL used for biopsy must be ≥ 2 cm in longest diameter (Please see requirements outlined in Appendix F).

- 7. ECOG performance status of 0 to 1 with no deterioration over the previous 2 weeks.
- 8. Adequate organ and bone marrow function measured within 14 days prior to first dose as defined in Table 6.

Note that one rescreen is permitted for participants if required, in line with Section 5.4.

Table 6 Criteria for Adequate Organ and Marrow Function

Parameter		Value	
	Haemoglobin	\geq 9.0 g/dL (5.59 mmol/L) with no blood transfusions (packed red blood cells) in the past 28 days.	
Haematological	Absolute neutrophil count	$\geq 1.5 \times 10^9 / L (1,500 \text{ per mm}^3)$	
	Platelet count	$\geq 100 \times 10^9 / L (100,000 \text{ per mm}^3)$ with no platelet transfusions in the past 10 days.	

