- All other lesions, including small lesions (longest diameter < 10 mm or pathological lymph nodes with ≥ 10 -mm to < 15-mm short axis diameter at baseline³)
- Previously irradiated lesions⁴
- Brain metastasis

The short axis is defined as the longest in-plane axis perpendicular to the long axis.

Lymph nodes with < 10-mm short axis diameter are considered non-pathological and should not be recorded or followed as NTLs.

Localized post-radiation changes that affect lesion size may occur. Therefore, lesions that have been previously irradiated are typically considered non-measurable and as NTL at baseline and followed up as part of the NTL assessment.

Special Considerations Regarding Lesion Measurability at Baseline:

- Bone lesions
 - Bone scan, PET scan, or plain X-ray are not considered adequate imaging techniques to measure bone lesions; however, these techniques can be used to confirm the presence or disappearance of bone lesions.
 - Lytic bone lesions or mixed lytic-blastic lesions, with identifiable soft tissue components, can be considered measurable if the soft tissue component meets the definition of measurability.
 - Blastic lesions are considered non-measurable.
- Cystic lesions thought to represent cystic metastases can be considered measurable lesions if they meet the criteria for measurability from a radiological point of view, but if non-cystic lesions are present in the same participant, these should be selected over cystic lesions as TLs.

RECIST v1.1 TL Selection at Baseline:

A maximum of 5 measurable lesions, with a maximum of 2 lesions per organ (including lymph nodes collectively considered as a single organ), representative of all lesions involved should be identified as TLs at baseline. Target lesions should be selected on the basis of their size (longest diameter for non-nodal lesions or short axis diameter for nodal lesions), but in addition should be those that lend themselves to reproducible repeated measurements. It may be the case that, on occasion, the largest lesion does not lend itself to reproducible measurement, in which circumstance the next largest lesion that can be measured reproducibly should be selected.

Lymph nodes, in any location (local/regional and distant), are collectively considered as a single organ, with a maximum of 2 lymph nodes as TLs. A bilateral organ (eg, adrenal glands), a segmented organ (eg, liver), or a multilobed organ (eg, lung) is each considered as a single organ.

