**Table 2: Populations for Analysis**

Population/Analysis set	Description	Endpoint/Output
Enrolled	All participants who sign the ICF	Disposition
Safety	All participants who receive any amount of IP.	Baseline and demographics Exposure Safety endpoints PK concentrations listings

Population/Analysis set	Description	Endpoint/Output
		PK parameters listings Immunogenicity listings PFS OS ctDNA
DLT Evaluable	Enrolled participants who complete the DLT evaluation period (defined as 21 days after receiving the first infusion of IP) with at least 75% dosing* and have completed safety evaluation requirements during the DLT evaluation period, as defined in the CSP  OR  Patients who experience any DLT during the DLT evaluation period.	DLT
Response Evaluable	All dosed participants who have measurable disease at baseline.	ORR DoR BoR DCR at 15 weeks Percentage change in tumour size
Pharmacokinetics	All participants who receive at least one dose of IP with at least one reportable concentration. **	PK concentrations PK parameters
Immunogenicity	All participants who receive at least one dose of IP who have a non-missing baseline ADA result and at least 1 non-missing post-baseline ADA result	Incidence of ADA ADA titer
Substudy 1 Population		
Interim Response Evaluable (Interim – Expansion only)	All dosed participants who had measurable disease at baseline and have had the opportunity for 2 on-treatment RECIST assessments (16 weeks, 6+9 weeks + 1 week window) or have had 2 on schedule tumour assessments.	ORR at interim DoR BoR at interim Tumour size
Pharmacodynamics	All participants who receive at least one dose of IP with baseline measurement and at least one	Change in circulating GDF15 serum levels (applicable for Part A and Part B only).

Population/Analysis set	Description	Endpoint/Output
	reportable pharmacodynamic measurement.	Change in CD8 tumour infiltration by IHC using baseline and on treatment samples (applicable to Part B only).

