#### **4.2.2.4 Primary Analysis of Secondary Endpoint**

ORR is based on a subset of all treated participants with measurable disease at baseline per the site investigator.

Summaries are produced that present the number and percentage of participants with a confirmed tumour response (CR/PR). The ORR is presented with a two-sided 90% CI using the Clopper-Pearson (exact probability) method. Participants that have missing OR assessments at all visits are considered as non-responders and are therefore counted in the denominator of ORR. The main analysis of ORR is based on the response evaluable set.

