### **Irradiated lesions/lesion intervention**

Previously irradiated lesions (i.e., lesion irradiated prior to entry into the study) are recorded as NTLs and should not form part of the TL assessment.

Any TL (including lymph nodes), which has had intervention during the study (for example, irradiation / palliative surgery / embolization but note this does not include protocol specified biopsies), are handled in the following way. Once a lesion has had intervention then it is treated as having intervention for the remainder of the study noting that an intervention most likely shrinks the size of tumours:

- Step 1: the diameters of the TLs (including the lesions that have had intervention) are summed and the calculation is performed in the usual manner. If the visit response is progressive disease, this remains as a valid response category.
- Step 2: If there is no evidence of progression after step 1, treat the lesion diameter (for those lesions with intervention) as missing. If progressive disease has not been assigned, then the visit response is set as NE.

At subsequent visits, the above steps are repeated to determine the TL and overall visit response. When calculating the previous minimum, lesions with intervention are treated as missing.

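### The SAP's RECIST appendix makes every previously irradiated lesion non-measurable and non-target, while protocol criterion 6a lets a progressed irradiated lesion be the qualifying target lesion, and the SAP does not say which rule governs response

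*SAP*

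**What the plan says.** Protocol 5.1, criterion 6, sets the entry condition: "Participants must have at least one lesion, that qualifies as a RECIST v1.1 TL at baseline". Sub-item 6a then says: "A previously irradiated lesion can be considered a TL if the lesion is well defined, measurable per RECIST v1.1, and has clearly progressed". The progression may have occurred on the latest treatment or since. Protocol Appendix F lists previously irradiated lesions among the non-measurable ones, but its footnote is qualified: "lesions that have been previously irradiated are typically considered non-measurable and as NTL at baseline".

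SAP 7.1 (Appendix A) carries no such qualification. Its definition reads "Measurable disease is defined as having at least one measurable lesion, not previously irradiated", and its paragraph on irradiated lesions says that lesions irradiated before entry "are recorded as NTLs and should not form part of the TL assessment". A participant without measurable disease is given a target-lesion visit response of NA. SAP section 2, which lists departures from the protocol, does not mention this one.

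SAP Table 2 defines the Response Evaluable set as "All dosed participants who have measurable disease at baseline". It serves ORR, DoR, BoR, DCR and percentage change in tumour size. The Interim Response Evaluable set carries the same condition. SAP 4.2.2.4 adds: "ORR is based on a subset of all treated participants with measurable disease at baseline per the site investigator". SAP 4.2.7.3 likewise takes measurable disease for tumour size from the investigator's eCRF entry. SAP 4.2.4.3 places DCR on the Response Evaluable population and names no source for the flag.

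**The concern.** A participant can be fully eligible under the protocol and yet have no target lesion under the SAP. Three things then depend on which text is programmed: who is in the denominator of the response endpoints, whether a partial response can be assigned at all, and which diameters enter the sum behind PR and progression. Two programmers working from the same data could reach different ORRs.

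The situation is plausible here. The population is pretreated, prior radiotherapy is collected at screening and summarised under SAP 4.1.7.2, and the June 2022 addendum sets washout rules for it. Participants qualifying only through an irradiated, progressed lesion are a selected group, so their loss or misclassification need not be neutral.

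**Working it through.** The plan gives no figure to reproduce: the number of such participants is not stated, and the Part C precision figures are redacted. The check is a comparison of texts, followed by an illustration of scale.

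**Step 1. The rules side by side**, for a lesion irradiated before entry that has clearly progressed:

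| Source | Status of the lesion |
|---|---|
| Protocol 5.1, 6a | May be a target lesion if well defined and measurable |
| Protocol Appendix F, list | Non-measurable |
| Protocol Appendix F, footnote | Typically non-measurable and non-target |
| SAP 7.1, Target Lesions | Cannot make disease measurable |
| SAP 7.1, Irradiated lesions | Non-target, outside the target-lesion assessment |

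The Appendix F footnote can be read together with 6a. The two SAP statements cannot.

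**Step 2. Follow a participant whose only target lesion qualifies under 6a.**

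- *Route A: Appendix A sets the Response Evaluable flag.* There is no measurable disease, so the participant leaves the set for ORR, DoR, BoR, DCR and tumour size, and the interim set.
- *Route B: the investigator's entry sets the flag, and Appendix A classes the lesion.* The participant stays in the denominator, but target-lesion response is NA. With target NA, SAP Table 12 allows only CR, SD, NE, NED or progressive disease. A shrinkage of 30% or more short of disappearance is scored SD. Such a participant can still count towards DCR if SD lasts at least 14 weeks. Best percentage change in tumour size is missing, or set to +20% in the situations listed in SAP 4.2.7.2. Progression is judged by the non-target criterion, not by the 20% and 5 mm rule, so the PFS date can also change.
- *Route C: the investigator's record sets both flag and lesion class.* The result follows 6a, and Appendix A as written is not applied.

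**Step 3. Participants with both kinds of lesion.** Let a be the summed diameters of non-irradiated target lesions and b those of irradiated ones, with subscripts 0 (baseline) and 1 (follow-up). Under 6a the change is (a1 + b1)/(a0 + b0) − 1. Under Appendix A it is a1/a0 − 1. The two agree only if a1/a0 = b1/b0. The participant stays in the set, but PR and progression can differ in either direction.

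**Step 4. Scale.** Inputs: 40 per expansion (SAP 3.3.7.2); two-sided 90% Clopper-Pearson interval (SAP 4.2.2.4). Assumed: 8 responders when all 40 are scored under 6a, and k = 1, 2 or 4 participants with only an irradiated target lesion. The limits are the 0.05 quantile of Beta(x, n − x + 1) and the 0.95 quantile of Beta(x + 1, n − x). Reference: 8/40 = 20.0% (10.4 to 33.2).

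| k | Route A, all k non-responders: 8/(40 − k) | Route A, all k responders: (8 − k)/(40 − k) | Route B, all k partial responders: (8 − k)/40 |
|---|---|---|---|
| 1 | 8/39 = 20.5% (10.6 to 34.0) | 7/39 = 17.9% (8.7 to 31.1) | 7/40 = 17.5% |
| 2 | 8/38 = 21.1% (10.9 to 34.8) | 6/38 = 15.8% (7.1 to 28.8) | 6/40 = 15.0% |
| 4 | 8/36 = 22.2% (11.6 to 36.5) | 4/36 = 11.1% (3.9 to 23.6) | 4/40 = 10.0% (3.5 to 21.4) |

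At the interim, triggered by the 20th participant in each expansion, one reclassified response among 20 is 1/20 = 5 percentage points.

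**The case against.** The strongest reply is that the analysis sections already defer to the investigator. ORR and tumour size take measurable disease from the site, and Table 10 in Appendix A defines target-lesion NA as no target lesions recorded at baseline. If the investigator records the irradiated lesion as a target lesion under 6a, one is recorded. The SAP describes no programmed step that strips it out. On that reading the Appendix A wording only repeats the protocol's default recording convention, and Route C is what happens.

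This reply has force on set membership. A reader might infer that participants enrolled under 6a necessarily leave the Response Evaluable set; SAP 4.2.2.4 and 4.2.7.3 do not support that. The reply does not settle lesion class, because SAP 7.1 says without exception that such lesions are kept out of the target-lesion assessment, and it is silent on whether a contrary site record prevails. DCR has no named source at all. Nor can one assume that sites apply 6a when completing the eCRF, since Appendix F, which investigators are told to use, lists irradiated lesions as non-measurable.

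It is also fair to say that the reach is narrow. Only participants with no other measurable lesion can leave the set, and membership for PFS and OS (Safety set) is untouched. ORR is a descriptive secondary endpoint with no hypothesis attached, and in the non-responder case the intervals overlap almost entirely.

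**Conclusion.** The contradiction between protocol criterion 6a and SAP 7.1 is in the text and is undeclared. If Appendix A is applied as written, an eligible participant whose only target lesion qualifies under 6a is either lost from the response endpoints or kept in them with no possibility of a partial response, and mixed cases can have a different sum of diameters. That conclusion is conditional on Appendix A being applied, because the SAP does not say whether it or the investigator's record prevails.

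The size is unknown. The counts in the working are assumptions. A reader might also infer that ORR is biased in a known direction. Route B can only take partial responders away, but Route A and the mixed cases can move ORR either way, so no net direction is shown. The point should be corrected before responses are derived. It does not threaten the design.

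**What to change.** 1. In SAP 7.1, add the exception *unless the lesion meets CSP 5.1 criterion 6a* to both the definition of measurable disease and the paragraph on previously irradiated lesions.
2. In SAP Table 2, state that the investigator's baseline eCRF record of measurable disease and target lesions sets the Response Evaluable flag, at the interim and the main analysis, for all response endpoints including DCR.
3. In protocol Appendix F, cross-reference 6a in the non-measurable list and its footnote, so that sites record these lesions consistently.

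If the sponsor does intend to exclude all irradiated lesions, that should instead be declared in SAP section 2 and reconciled with 6a. The cost is a few SAP sentences and one cross-reference at the next protocol amendment. Settling it before responses are derived avoids a choice made after the results are seen.
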